10.2 Statistical methods for time-to-event data

The analysis of time-to-event data are conducted using Kaplan-Meier estimates of events over time (including graphical representation). Intervals will be displayed on plots up to the time point where at least 10% of subjects are still at risk.

10.2.1 Time to event

Estimates of the event rate are obtained for each treatment group using the Kaplan-Meier method as implemented in SAS Proc Lifetest. The graphical representation follows the recommendations from Pocock [Pocock 2002]. Two-sided CIs at specific timepoints are constructed, with confidence limits calculated using Greenwood's formula for the estimate of the standard error. Median time to event (as well as 25th and 75th percentiles) for each group are provided with the corresponding two-sided CIs calculated using the method of Brookmeyer [Brookmeyer 1982].

11 GENERAL DEFINITIONS AND DERIVATIONS

11.1 Dates, times and days

Study treatment start date see definition in Section 5.3.1.1.

End-of-Treatment (EOT) / Study treatment end date, defined as the latest study treatment end date as recorded on the Study Drug Log eCRFs [see Section 5.3.1.1].

End-of-Study (EOS) date is defined as the 'Date of Subject Decision' (if reason for study discontinuation was 'Subject Decision'), 'Date of Physician Decision' (if reason for study discontinuation was 'Physician Decision') collected on the 'Study Discontinuation' eCRF, or 'Date of recorded last study visit / assessment' (if reason for study discontinuation was 'Sponsor Decision'), unless a subject is lost to follow-up or dies, in which case 'Date of last successful contact' from the Study Discontinuation eCRF or 'Date of Death' from Death eCRF are used. If missing, the last recorded visit date (i.e., the latest assessment date within any visit) is considered as the EOS date [see Section 5.1.6].

Screening date defined as the visit date of the last available screening visit, i.e., date of Visit 1A for re-screened subjects, date of Visit 1 for all others.

Study Day refers to the number of days elapsed since randomization date plus 1 (e.g., Study Day 1 is the day of randomization). For dates prior to randomization, study day is the negative number of days elapsed between the date under consideration and the day of randomization. Therefore, the study day is always different from 0.

For efficacy analyses also referred to as 'Day'.

Treatment Day refers to the number of days elapsed since study treatment start date plus 1 (e.g., Treatment Day 1 is the day of study treatment start). For dates prior to study treatment start, treatment day is the negative number of days elapsed between the date under consideration and the day of study treatment start. Therefore, it is always different from 0.

For safety analyses also referred to as 'Day'.

11.2 Analysis period definitions

11.2.1 Efficacy study periods

The ‘Efficacy Study Period’ of primary interest in this study is the period from randomization up to the EOS date, defined as: [Randomization; EOS].

11.3 Re-assignment of premature EOT visits / Visit windowing

For all parameters unless stated below: For subjects who discontinued study drug prematurely with available premature EOT visit, the visit may be re-assigned to a scheduled visit as follows:

- Scheduled nominal visits, e.g., Week xx, are identified based on the eCRF recorded nominal visit label. Note that the eCRF allows for considering a visit under multiple visit labels, e.g., a Follow-up 1 or a Relapse visit can be considered in addition a Week xx visit. This 2nd visit label is collected on the Visit Summary eCRF under ‘Corresponding visit’. In selecting results for a nominal scheduled visit both visit labels are considered. Priority is given to the 1st visit label, afterwards to the 2nd visit label. If at a scheduled nominal visit no result is available, premature EOT remapping is applied.
- If a result is missing for a scheduled visit, it can be replaced with a result from a premature EOT visit available in the respective visit window [see [Table 6](#) and [Table 7](#)].

Table 6 Premature end of treatment remapping (except MRI)

Visit window	Nominal value Day	Lower limit for Day	Upper limit for Day
Week 2	15	2	22
Week 4	29	23	70
Week 12	85	71	126
Week 24	169	127	210
Week 36	253	211	294
Week 48	337	295	378
Week 60	421	379	462
Week 72	505	463	546
Week 84	589	547	630
Week 96	673	631	714
Week 108	757	715	798
Week 120	841	799	882
Week 132	925	883	966
Week 144	1009	967	1050
Week 156	1093	1051	Open end

Day refers to treatment day, i.e., days from study treatment start.

Table 7 Premature end of treatment remapping (MRI)

Visit window	Nominal value Day	Lower limit for Day	Upper limit for Day
Week 24	169	85	252
Week 48	337	253	420
Week 72	505	421	588
Week 96	673	589	756
Week 120	841	757	924
Week 144	1009	925	1050
Week 156	1093	1051	Open end

Day refers to treatment day, i.e., days from study treatment start.

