1 INTRODUCTION

This Statistical Analysis Plan (SAP) describes the analyses and presentation of the key efficacy, safety and pharmacodynamic (PD) endpoints for the synoptic clinical study report (CSR) of the AC-058B302 study (POINT).

Separate SAPs (not described here) are developed for analyses on:

- Vaccination specific antibody titers.

Source data for the analyses are provided as Statistical Analysis Software (SAS[®]) data sets according to Clinical Data Interchange Standards Consortium (CDISC) Study Data Tabulation Model (SDTM).

On 26 November 2019 it was decided to prematurely terminate the study.

This decision was made following the recommendation from the Independent Data Monitoring Committee (IDMC) at the IDMC meeting on 10 September 2019 to further evaluate the feasibility of the AC-058B302/POINT study. The study started enrolling subjects in March 2017, and after 2.5 years of recruitment had enrolled 136 subjects (22% of the targeted population). The IDMC recommendation was as follows:

- The IDMC recognized the Sponsor's efforts to increase enrolment but these were not successful. Therefore, the IDMC members are concerned that the study will not be finished in an adequate timeframe which will impair a proper assessment of safety, efficacy, and feasibility.
- With the current recruitment rate the IDMC members regard the study as futile.
- IDMC members request arguments against futility from the sponsor to continue the study as per protocol.

As a result of this evaluation, the Sponsor concluded that the current study design with the required sample size is unlikely to achieve the study objectives, and therefore prematurely terminated the study.

Following the decision to prematurely terminate the study, it was decided also to produce a synoptic CSR of the key efficacy and safety data only.

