2 STUDY DESIGN AND FLOW

This is a prospective, multicenter, randomized, double-blind, parallel-group, add-on, placebo-controlled, Phase 3, superiority study. The study is designed to compare the efficacy, safety, and tolerability of add-on therapy with ponesimod 20 mg vs placebo in adult subjects with active relapsing multiple sclerosis (RMS) who are treated with dimethyl fumarate (DMF; Tecfidera[®]).

It was planned to randomize approximately 600 subjects who had been receiving DMF twice daily for at least 6 months in a 1:1 ratio to ponesimod 20 mg or placebo (approximately 300 subjects per

arm). Randomization is stratified by baseline Expanded Disability Status Scale (EDSS) score ($EDSS \leq 3.5$, $EDSS > 3.5$).

At the time of the decision to terminate the study, a total of 136 subjects had been randomized at 54 sites (randomized subjects) in 17 countries in North America, and Eastern and Western Europe regions.

Following the decision to terminate the study:

[figure not shown]
- Subjects in screening at the time of the announcement were required to be screen failed;
- Subjects on study treatment were required to perform the End-of-Treatment (EOT) visit within 8 weeks and the follow-up visits;
- Subjects in the post treatment observation period (PTOP) were required to perform the Visit 18A within 4 weeks.

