5.1.5 Subject study treatment completion status

Due to the early termination of the study, no treatment completers as per protocol are expected as no subjects will have completed 156 weeks of treatment / 60 weeks of treatment following randomization of the last subject.

Subjects who complete study treatment up to study termination are defined as those meeting any of the following conditions:

- a record in the eCRF ‘Maintenance Ponesimod/Placebo’ form with reason for treatment end given as ‘Completed as per protocol’;
- reason ‘Sponsor decision’ with sub-reason ‘Study termination’ (for question ‘Study treatment stopped due to’) is reported on the eCRF form ‘Premature Discontinuation of Study Treatment’,
- the reason for treatment end is documented as ‘Study Closure Announcement by Sponsor’ on the eCRF ‘Up-titration Ponesimod/Placebo’ or ‘Maintenance Ponesimod/ Placebo’.

A subject is considered to have prematurely discontinued from the study treatment if:

- at least one reason (‘Study treatment stopped due to’) which is not ‘Sponsor decision’ with sub-reason ‘Study termination’ is reported on the eCRF form ‘Premature Discontinuation of Study Treatment’ and/or
- the reason for treatment end is documented as ‘Premature Permanent Discontinuation’ on the eCRF ‘Up-titration Ponesimod/Placebo’ or ‘Maintenance Ponesimod/ Placebo’.

The date of treatment discontinuation is the last date study drug was taken [defined in Section 5.3.1.1]. In case of a (partially) missing discontinuation date, the date is imputed with the EOS date as defined in Section 5.1.6, or with the upper limit of the partial date if prior to EOS.

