5.4.4.2 Change in EDSS from baseline by visit up to EOS

Absolute changes from baseline in EDSS score by visit are derived, based on the overall EDSS score as reported by the investigator in the eCRF. For subjects prematurely discontinuing treatment, results collected during PTOP are considered at the corresponding nominal visit in the same way as for subjects completing treatment as planned (e.g., by visit analysis at Week 24, considers both ‘Week 24’ and ‘PTOP Week 24’ visits). Baseline EDSS is defined as in Section 5.4.2.1.

On-treatment EDSS assessments will be flagged, i.e., EDSS assessments performed after study treatment start (date/time) and prior to EOT + 7 days.

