11.4 Summaries by visit

Visit based safety and PD assessments are generally summarized according to the nominal visit. Except for Visit 18 (EOT/Week 156) in subjects prematurely discontinuing study treatment, Visit 19 (FU7d, Day 7 follow-up assessment for lymphocyte subset only), and Visit 20 (FU, Day 30 follow-up assessment). Those are derived following the rules below:

- Premature EOT visits are re-assigned following the visit windowing described in Section 11.3
- Day-7 follow-up assessment: Any assessment within EOT date + 6 days and EOT date + 15 days. If multiple assessments fall into that period, the one corresponding to the regular FU7d visit (Visit 19) is selected, if none of the multiple assessments corresponds to that visit, the one closest to EOT date + 7 days is selected, if there are two closest assessments, the later one is selected.
- Day-30 follow-up assessment: Any assessment within EOT date + 16 days and EOT date + 37 days. If multiple assessments fall into that period, the one corresponding to the regular FU visit (Visit 20) is selected, if none of the multiple assessments corresponds to that visit, the one closest to EOT date + 30 days is selected, if there are two closest assessments, the later one is selected.

In addition, the ‘Last on-treatment’ assessment is flagged. This is defined to be the latest assessment prior to or on EOT date + 1 day (last on treatment may come from a scheduled or an unscheduled visit).

Summaries by visit are presented by Baseline (derived), and further scheduled nominal visits up to Week 156 (irrespectively if conducted during PTOp or not), Last on-treatment, and derived Follow-up visits (FU7d, FU). Generally, by visit tables are tabulating the baseline and nominal and derived visits as follows:

- Baseline (Note: This is not a nominal visit but the derived baseline; see Section 5.5.1)
- Visit 4 - Week 2

- Visit 5 - Week 4
- Visit 6 - Week 12
- Visit 7 - Week 24
- Visit 8 - Week 36
- Visit 9 - Week 48
- Visit 10 - Week 60
- Visit 11 - Week 72
- Visit 12 - Week 84
- Visit 13 - Week 96
- Visit 14 - Week 108
- Visit 15 - Week 120
- Visit 16 - Week 132
- Visit 17 - Week 144
- Visit 18 - Week 156
- Last on-treatment (derived; see Section 5.5.1)
- Day-7 follow-up (derived) (lymphocyte subset only)
- Day-30 follow-up (derived)

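### EOT visits caused by the study termination are not clearly covered by the re-mapping rule, and early Visit 18A is not covered at all, so both can be tabulated as Week 156, which no subject reached

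*SAP*

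**What the plan says.** Section 2 describes the wind-down. Subjects on treatment were to have their EOT visit (Visit 18) within 8 weeks. For the others, "Subjects in the post treatment observation period (PTOP) were required to perform the Visit 18A within 4 weeks". Table 4 labels Visit 18A as W156A.

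Section 5.1.5 introduces a class created by the termination: "Subjects who complete study treatment up to study termination are defined as those meeting any of the following conditions". The conditions include sponsor decision with study termination as sub-reason. Premature discontinuation is defined separately. It needs a reason other than study termination, or a drug-log entry of permanent premature discontinuation. The same section expects no one to have completed 156 weeks.

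Section 11.3 then opens its windowing rule with "For subjects who discontinued study drug prematurely with available premature EOT visit, the visit may be re-assigned to a scheduled visit". A re-mapped result is used only where the scheduled result is missing. Section 11.4 tabulates safety and PD data by nominal visit, with the exception "Except for Visit 18 (EOT/Week 156) in subjects prematurely discontinuing study treatment", and lists Visit 18 as Week 156 in both its safety and its efficacy visit lists. For EDSS, Section 5.4.4.2 adds that "results collected during PTOP are considered at the corresponding nominal visit in the same way as for subjects completing treatment as planned".

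**The concern.** Section 5.1.5 was adapted to the termination; Sections 11.3 and 11.4 were not. If *prematurely* in Section 11.3 has the meaning given in Section 5.1.5, an EOT visit forced by the termination is not a premature EOT visit. It is not windowed and stays in the Week 156 row. Visit 18A is not an EOT visit at all, so the rule never reaches it, and its nominal label is Week 156.

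The Week 156 row would then pool subjects treated for anything from a few weeks to almost three years. A termination EOT scan lying in, say, the Week 48 window could not stand in for a missing Week 48 scan, although Sections 5.4.3 and 5.4.3.1 allow a re-mapped scan to do so. Two programmers working from the same text could produce different by-visit tables.

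**Working it through.** **Inputs.**
- Section 1: "The study started enrolling subjects in March 2017" (no day given, so 1 and 31 March are both used), and "On 26 November 2019 it was decided to prematurely terminate the study".
- Section 2: "a total of 136 subjects had been randomized at 54 sites"; EOT visit within 8 weeks, Visit 18A within 4 weeks. The starting point of these periods is not spelled out; the decision date is assumed.
- Tables 6 and 7: Week 156 has nominal Day 1093 and a window from Day 1051 with no upper limit. Day means treatment day, that is, visit date − treatment start date + 1.

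**The plan's own figure.** Nominal Day = 7 × 156 + 1 = 1093, as in Tables 6 and 7.

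**Latest possible visits.**
- EOT: 26 Nov 2019 + 56 days = 21 Jan 2020. From 1 March 2017 to 26 Nov 2019 is 1000 days, so the latest treatment day is 1000 + 56 + 1 = 1057 (151.0 weeks). For a 31 March start it is 1027 (146.7 weeks).
- Visit 18A: 26 Nov 2019 + 28 days = 24 Dec 2019, giving Day 1029 (147.0 weeks) or Day 999 (142.7 weeks).

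Neither visit can reach Day 1093, which agrees with Section 5.1.5. A subject starting on 1 March 2017 would have needed an EOT visit 1093 − 1057 = 36 days after 21 Jan 2020. Visit 18A cannot reach even the Day 1051 edge of the window. An EOT visit can do so only for a subject who started by 7 March 2017 (21 Jan 2020 minus 1050 days).

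**Where termination EOT visits would fall if windowed.** Assume uniform accrual up to the decision, everyone still on treatment, and EOT at the 8-week limit. Treatment days then run evenly from 57 to 1057 (first start 1 March) or from 57 to 1027 (first start 31 March).

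| | Start 1 March | Start 31 March |
|---|---|---|
| Median day | (57 + 1057)/2 = 557 | (57 + 1027)/2 = 542 |
| At or before the Week 96 window (Day 714) | (714 − 57)/1000 = 66% | (714 − 57)/970 = 68% |
| In the Week 156 window (Day 1051 or later) | (1057 − 1051)/1000 = 0.6%, × 136 = 0.8 subjects | 0 |

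With EOT at 0 or 4 weeks, no subject enters the Week 156 window.

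**How many subjects.** The SAP does not give the number on treatment or in post-treatment observation at termination. If 10%, 30% or 50% of the 136 had already stopped treatment (an assumed range), 122, 95 or 68 termination EOT visits would be involved on the literal reading.

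**Which outputs use the label.**
- Termination EOT visit: by-visit ECG, vital signs, laboratory, lymphocyte, spirometry, EDSS and MRI summaries.
- Visit 18A: mainly by-visit EDSS and MRI. Sections 9.9.3 to 9.9.6 restrict by-visit safety tables to treatment-emergent results (up to EOT + 15 days), and post-treatment observation follows the 30-day follow-up visit. Lymphocyte subsets may also be affected, since they are sampled at 18A and Section 9.10.2 states no such restriction.
- Cumulative MRI at Weeks 24, 48, 72 and 96: only where the scheduled scan is missing.

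**The case against.** The best counter-argument concerns the EOT visits. Section 11.3 does not cite Section 5.1.5, which is a disposition definition. The termination reason is itself recorded on the eCRF form for premature discontinuation. Section 2.1.1 has the treatment period run to Week 156 or to 60 weeks after the last randomization, so in that sense nobody completed it. The EOS definition in Section 11.4 knows only completers of the treatment period and premature discontinuers. On this reading a termination EOT visit is a premature EOT visit, and Section 11.4 already says twice that such a visit is not shown as Week 156 unless the windows put it there. This reading is reasonable and cannot be ruled out. What remains is that Section 5.1.5 points the other way and the plan does not settle the matter. The argument does nothing for Visit 18A.

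A reader might also infer more than the text supports:
- *That most subjects' last data are mislabelled.* The number affected is not given, and the Last on-treatment and Day-30 follow-up rows are derived from actual dates.
- *That the correct windows lose each subject's last observation.* Re-mapping only fills a missing scheduled result, so a subject whose scheduled visit in that window was done would contribute nothing extra under the fix either.
- *That efficacy conclusions are at risk.* The relapse rate, time to relapse, confirmed disability accumulation and lesion counts to end of study use actual dates or sum scans whatever their label. Week 156 is not one of the cumulative MRI time points.

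**Conclusion.** The plan is incomplete on this point and, read literally, wrong. For Visit 18A the gap exists on any reading: early EDSS and MRI results default to Week 156, although the latest such visit is about Day 999 to 1029. For termination EOT visits the outcome depends on which meaning of *prematurely* is applied. Under the SAP's own definition they too stay at Week 156, with a latest day of about 1027 to 1057 against nominal Day 1093. At most about one subject would belong in that row.

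The day ranges assume that the 4 and 8 weeks run from the decision date and that treatment began no earlier than March 2017. The figure of one subject also assumes uniform accrual. The number of mislabelled visits cannot be derived from the document.

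The damage is confined to by-visit summaries, which are mainly descriptive, and to which results may fill missing scheduled visits. This should be fixed, but it does not bear on the primary or secondary efficacy estimates.

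**What to change.** In Sections 11.3 and 11.4, state that Tables 6 and 7 apply to every Visit 18 and every Visit 18A performed before planned Week 156, whatever the reason. Name explicitly the subjects whom Section 5.1.5 defines as completing treatment up to study termination. Keep the existing rule that a re-mapped result only fills a missing scheduled result. Allow the Week 156 row to be filled only by assessments on Day 1051 or later. Table 7 starts at Day 85, so it should also be said that an earlier termination scan enters no by-visit row.

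The cost is a sentence or two of SAP text and one programming condition. No new data are needed.

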Premature EOT visits are mapped to and summarized within a scheduled visit following the window approach described in Section 11.3; they will not be summarized as “Visit 18 - Week 156” unless they are mapped to this visit as per approach described in Section 11.3.

As per protocol, total lymphocyte counts will be assessed every 4 weeks up to Week 24 (i.e., there are 3 protocol mandated between-visit assessments for those tests at Week 8, Week 16, and Week 20 when no regular visit is scheduled).

These assessments are considered scheduled and are included in corresponding by-visit tabulations labeled as follows:

- Additional Visit - Week 8
- Additional Visit - Week 16
- Additional Visit - Week 20

Visit-based efficacy are summarized according to the nominal visit up to EOS, irrespective if conducted during PTOP or not:

- Baseline (Derived)
- Visit 4 - Week 2
- Visit 6 - Week 12
- Visit 7 - Week 24
- Visit 9 - Week 48
- Visit 11 - Week 72
- Visit 13 - Week 96

- Visit 15 - Week 120
- Visit 17 - Week 144
- Visit 18 - Week 156

Premature EOT visits are mapped to and summarized within a scheduled visit following the window approach described in Section 11.3; they will not be summarized as “Visit 18 - Week 156” unless they are mapped to this visit as per approach described in Section 11.3.

EOS visit is defined for efficacy endpoints and JCV:

- For subjects who complete the treatment period, and for subjects who prematurely discontinue study treatment and do not enter the PTOp, the EOS visit corresponds to the 30 day follow-up visit (FU) for efficacy endpoints, and for the last available visit for JCV.
- For subjects who prematurely discontinue study treatment and enter the PTOp period, the EOS visit corresponds to the last visit of the PTOp.

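### Table 6 places the Week 4/Week 12 boundary at Day 70/71 instead of the midpoint, Day 57, so premature end-of-treatment results on Days 58–70 cannot fill the nearer Week 12 visit

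*SAP*

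**What the plan says.** SAP Section 11.3 gives day windows for re-assigning a premature EOT visit to a scheduled visit: Table 6, whose caption begins "Premature end of treatment remapping (except MRI", for everything except MRI, and Table 7 for MRI. The windows are on the treatment-day scale ("Day refers to treatment day, i.e., days from study treatment start"). In Table 6, Week 4 has nominal Day 29 and limits 23 and 70. The next two rows, as nominal day, lower limit and upper limit, are "Week 12 85 71 126" and "Week 24 169 127 210". There is no Week 8 row.

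The replacement is conditional. When a scheduled visit lacks a result, "it can be replaced with a result from a premature EOT visit available in the respective visit window". Section 11.4 then states the outcome without that condition: "Premature EOT visits are mapped to and summarized within a scheduled visit following the window approach described in Section 11.3".

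Section 11.4 also treats the extra total lymphocyte counts at Weeks 8, 16 and 20 as scheduled and gives them their own table rows, for example "Additional Visit - Week 8". Table 6 has no windows for them.

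**The concern.** Nearly every limit in the two tables follows a nearest-visit pattern. One does not, and the SAP does not explain it. A subject who stops treatment early and has the EOT visit in the third month is closer to Week 12 than to Week 4, yet the table allows that result to be used only for Week 4.

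What is at stake is where early discontinuers' last results appear in the by-visit tables. Three sets of parameters have no Week 4 slot to receive the value:

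- **Spirometry** is scheduled at Baseline, Week 12, Week 48 and every 48 weeks after that (Section 5.5.13.1). Its by-visit summary relies on this remapping (Section 9.9.6).
- **Lymphocyte subsets** are sampled at Baseline, Week 12 and Week 24, then later visits (Section 5.6.2).
- **EDSS** is assessed every 12 weeks (Section 5.4.2.1), and the efficacy visit list in Section 11.4 goes from Week 2 to Week 12 with no Week 4 row.

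For these, an EOT result on Days 58–70 is directed to a visit at which the parameter is not planned or not tabulated, while Week 12 may stay empty.

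**Working it through.** **Inputs.** Nominal days and limits from Table 6 and Table 7 (Section 11.3).

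**Formula.** Midpoint = (nominal day of earlier visit + nominal day of later visit) / 2. A boundary counts as a midpoint if that day is either the upper limit of the earlier window or the lower limit of the later one.

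| Boundary (Table 6) | Midpoint | Stated upper/lower | Midpoint? |
|---|---|---|---|
| Week 2/4 | (15 + 29)/2 = 22 | 22/23 | yes, tie to earlier visit |
| **Week 4/12** | **(29 + 85)/2 = 57** | **70/71** | **no** |
| Week 12/24 | (85 + 169)/2 = 127 | 126/127 | yes, tie to later visit |
| Week 24/36 | (169 + 253)/2 = 211 | 210/211 | yes, tie to later visit |
| … in steps of 84 days | 295, 379, …, 967 | 294/295, 378/379, …, 966/967 | yes, tie to later visit |
| Week 144/156 | (1009 + 1093)/2 = 1051 | 1050/1051 | yes, tie to later visit |

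Thirteen of the 14 boundaries in Table 6 are midpoints. All six in Table 7 are too (253, 421, 589, 757, 925, 1051).

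**Distances around the disputed boundary.**

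| Treatment day | Days from Week 4 (Day 29) | Days from Week 12 (Day 85) |
|---|---|---|
| 57 | 28 | 28 |
| 58 | 29 | 27 |
| 70 | 41 | 15 |
| 71 | 42 | 14 |

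Day 57 is an exact tie. The days strictly nearer Week 12 but inside the Week 4 window are 58–70, which is 70 − 58 + 1 = 13 days. As written, the Week 4 window extends 29 − 23 = 6 days before its nominal day and 70 − 29 = 41 days after it.

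**What happens to a result on those days.**

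- *Parameter measured at Week 4, such as the safety laboratory (Section 5.5.12).* A subject still on treatment near Day 58 will normally have a Week 4 result, so the EOT value replaces nothing there, and the window stops it filling Week 12. It enters Week 4 only if that result is missing.
- *Parameter with no Week 4 assessment or row.* The value either becomes a stray Week 4 entry or has no row at all. In both cases it cannot fill Week 12.
- *Last on-treatment row.* This takes the latest assessment up to EOT + 1 day (Sections 5.5.1 and 11.4). The EOT visit window is + 7 days (Table 3), so a visit 2 to 7 days after the last dose misses that row.

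**Limits for the extra lymphocyte visits.** Nominal days on the same scale are Week 8 = 57, Week 16 = 113 and Week 20 = 141. Midpoints: (29 + 57)/2 = 43; (57 + 85)/2 = 71; (85 + 113)/2 = 99; (113 + 141)/2 = 127; (141 + 169)/2 = 155.

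**The case against.** The SAP states no midpoint or nearest-visit rule. It lists limits that neither overlap nor leave gaps. Another pattern also fits: every closed upper limit from Week 4 to Week 144 is the nominal day plus 41 (29 + 41 = 70, 85 + 41 = 126, 1009 + 41 = 1050). It is therefore fair to call this an unexplained choice rather than a computational error. But from Week 12 on, visits are 84 days apart, so nominal + 41 is the midpoint limit. Between Week 4 and Week 12 the gap is only 56 days, and the same 41 days runs well past halfway.

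Several stronger readings are tempting but are not supported:

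- *That EOT results on these days are generally reported as Week 4.* Remapping requires a missing scheduled result, so this is the exception.
- *That the values are lost.* They may appear under Last on-treatment, and results up to EOT + 15 days count in the treatment-emergent abnormality tables (Sections 5.5.1 and 9.9.3 to 9.9.6). Section 11.3 also lets a follow-up visit carry a second, scheduled-visit label, so Week 12 is not always empty.
- *That the Week 4 reference for the lymphocyte-decrease flag is contaminated.* Section 5.6.1 refers to Visit 5 and nowhere says that a remapped EOT value takes its place.
- *That a Week 8 row was merged into Week 4.* Day 71 is the Week 8/Week 12 midpoint, so this is possible, but the SAP does not say so.
- *That many subjects are affected because discontinuations cluster early.* The SAP gives no distribution of discontinuation times.

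Leaving Weeks 8, 16 and 20 out of the remapping is also a coherent choice. If a Week 8 lymphocyte window were added, the Week 12 lower limit for that parameter would remain Day 71.

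**Conclusion.** The concern holds as a minor inconsistency. The Week 4/Week 12 limit is the only one of the 20 boundaries in the two tables that is not a midpoint (14 in Table 6, six in Table 7). It is 13 to 14 days late, depending on how the tie at Day 57 is resolved. The usual consequence is that an EOT result from Days 58–70 does not fill an empty Week 12, mainly for spirometry, lymphocyte subsets and EDSS change by visit.

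Only descriptive by-visit summaries change. The annualized relapse rate, time to first confirmed relapse and confirmed disability accumulation do not use Table 6, and the MRI endpoints use Table 7. The number of subjects concerned cannot be derived from the SAP. With 136 randomized and a 13-day range it is probably small.

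The conclusion assumes that the intended rule is nearest visit. The other boundaries imply this, but the SAP does not state it.

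**What to change.** In Table 6, set Week 4 to Days 23–56 and Week 12 to Days 57–126. This gives the tie at Day 57 to the later visit, as at every boundary from Week 12/24 onward. If Day 70/71 is deliberate, state the reason instead.

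If the Week 8, 16 and 20 total lymphocyte counts are meant to receive remapped EOT values, add a separate lymphocyte table with midpoint limits: Week 4, Days 23–42; Week 8, 43–70; Week 12, 71–98; Week 16, 99–126; Week 20, 127–154; Week 24, 155–210. If not, one sentence saying so is enough.

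The cost is two numbers in one table, plus a short extra table if wanted, and the matching change in the visit-windowing program. No data collection or inferential analysis is affected.
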